3.1.3 Internal Monitoring Committee and Scientific Oversight Committee

An IMC will be established to monitor patient safety throughout the study and provide a recommendation on the dose to be taken forward into the expansion stage after

completion of the dose-escalation stage. The IMC will include Sponsor representatives from Clinical Science, Biostatistics, Safety Science, and Clinical Pharmacology. IMC members should not have regular contact with the sites as part of their responsibilities.

In addition to the ongoing assessment of the incidence and nature of DLTs, adverse events (particularly Grades ≥ 3), serious adverse events, deaths, and laboratory abnormalities by the investigator and the Medical Monitor, the IMC will review all necessary cumulative data at regular intervals during the study (including prior to suspension dose escalation and prior to initiation of expansion cohorts). Ad hoc meetings may be called in addition to scheduled meetings, as necessary, to obtain IMC recommendations on management of any new safety issues.

A Scientific Oversight Committee (SOC), which will consist of experts external to the Sponsor (including at least two members not involved in study activities), will also be established for this study. The SOC will enhance safety monitoring and leverage external experts' scientific expertise by providing advice on data interpretation. The SOC will function as a consultative body to the Sponsor, providing individual expert opinions.

Specific operational details, such as committee composition, frequency and timing of meetings, and member roles and responsibilities, will be detailed in an IMC and SOC Charter.

3.2 END OF STUDY

The end of this study is defined as the date when the last patient, last visit (LPLV) occurs, or 5 years after the last patient is enrolled, whichever occurs first. The Sponsor reserves the right to present interim data to health authorities for compliance purposes.

For an individual patient the completion of the study (i.e., the last visit) will occur when the patient withdraws consent, has completed follow-up, has been lost to follow-up, dies, or when the trial is stopped.

The primary analysis will be conducted after the enrollment has been completed and all enrolled patients have been followed for at least 12 months. Clinical Study Report (CSR) will be submitted to health authorities.

3.3 RATIONALE FOR STUDY DESIGN

3.3.1 Rationale for Cobimetinib Dose and Schedule

Cobimetinib will be administered by mouth once daily on Days 1–21 of each 28-day treatment cycle. The traditional starting point for pediatric oncology Phase I studies of cytotoxic agents is 80% of the adult dose (Lee et al. 2005) and for targeted agents according to the toxicity profile 80%–100% of the adult dose appears safe (Paoletti et al. 2013). In the dose-escalation stage, the first cohort of 3 patients treated with tablets will receive cobimetinib at a dose of 0.6 mg/kg, or approximately 80% of the adult Phase III dose.

The mean elimination $T_{1/2}$ of most substrates approaches adult levels at 2–6 months of age. In vitro data suggest that, although liver enzymes in general have not matured fully, a significant amount and activity of enzymes are present at this age (Bartelink et al. 2006). In vitro data indicate that cobimetinib is a substrate of CYP3A4 and UGT2B7, both of which are expressed before or soon after birth. The activity of both CYP3A4 and UGT2B7 reaches 100% of adult activity by 1 year of age (Kearns et al. 2003). Given the maturation profile of the two enzymes principally involved in cobimetinib metabolism, significant differences in cobimetinib metabolism are not expected to be observed among pediatric patients, even those as young as 6 months of age. Per Section 3.1.1.2, patients < 1 year of age will not be eligible for enrollment until a safety and PK assessment of the first 6 patients treated with suspension for at least one cycle of therapy has been conducted and until all available pediatric data from tablet and suspension cohorts has been reviewed by the IMC.

If a drug is mainly metabolized by UGT or CYP2D6, the plasma clearance seems to be correlated with body weight (Bartelink et al. 2006). Thus, doses in this study will be based on patient body weight.

3.3.1.1 Rationale for Tablet and Suspension Dosing Strategy

Cobimetinib has good solubility in water (0.74 mg/mL, at 37°C). A mass balance study in humans has shown that the fraction of dose absorbed is 0.88, indicating high fraction absorbed and hence permeability. Given the high solubility and permeability of cobimetinib, differences due to formulation change are not anticipated. During development of cobimetinib in adult populations, it was seen that different formulations provided comparable exposures (see cobimetinib Investigator's Brochure), and that cobimetinib absorption was not dissolution-rate limited. Hence, the suspension is expected to provide similar exposures as would be obtained upon administration of the tablet, and therefore equivalent doses administered to pediatric patients will provide comparable exposures. As bioequivalence has not been directly proven between the existing tablet and powder for suspension formulations in a relative bioavailability study, the Sponsor will initiate dose escalation for the suspension at least one dose level below that of the tablet MTD/MAD to ensure study drug administration via suspension does not result in overexposure or excessive toxicity.

Both tablet and suspension formulations are being utilized to ensure adequate age-appropriate dosing for the study. Enrollment to receive the tablet will be restricted to patients ≥ 6 years of age due to the size of the tablet. Enrollment to receive the tablet will further be restricted to patients weighing ≥ 20 kg, because tablet dosing (defined in [Appendix 10](#)) in patients < 20 kg could potentially cause excessive variation in cumulative administered dose per kilogram ($> 10\%$) within a dose level cohort.

To ensure that patients treated with tablets receive a cumulative dose most closely approximating their body weight, patients will be assigned a cumulative weekly dose in 20-mg increments, with distribution of tablets as evenly as possible throughout the week. For example, if a patient's dose is 60 mg in a week, the dosing would be 20 mg on Days 1, 3, and 5 of that week. Given the $T_{1/2}$ of cobimetinib (approximately 2 days), the intermittent dosing of cobimetinib is not expected to result in significant fluctuations in the average cobimetinib concentrations, and steady state exposures will be achieved approximately 10 days after start of dosing.

3.3.2 Rationale for Patient Population

The late-phase program of cobimetinib in adults is focused on indications with limited existence in children, thus significantly reducing the population of pediatric patients potentially able to receive the drug. Given the occurrence of alterations in the RAS/RAF/MEK/ERK pathway in a large range of pediatric malignancies, the pursuit of a broad mechanism-of-action-derived approach to include pediatric tumors may maximize the opportunity to determine which pediatric patients may benefit from treatment with cobimetinib. Importantly, the safety of cobimetinib as a single agent must be demonstrated and toxicity must be analyzed to provide treating physicians with clear guidance for administration of cobimetinib and monitoring of patients in the pediatric setting. With this in mind, the trial will draw from a broad spectrum of pediatric tumor types, each of which has evidence of growth promotion through the RAS/RAF/MEK/ERK pathway either in nonclinical model systems or retrospective clinical tumor analyses.

The Sponsor expects that the majority of enrolled patients will be < 18 years of age. Patients even as young as 6 months of age may experience tumor types such as neuroblastoma for which cobimetinib is a rational potential therapy, and these patients will be included in the trial upon availability of a suspension formulation. However, there may be young adult patients with "pediatric-type" tumors who are treated in pediatric oncology facilities. In a specific analysis of adolescent and young adult (AYA) patients in the United States, limited clinical trial participation correlated with the relative lack of improvement in survival prolongation and cancer death rates (Bleyer et al. 2006). The lower participation of AYAs in clinical trials has created significant knowledge gaps with respect to cancer biology, treatment, and other factors affecting the survival of AYAs with cancer. As part of the Sponsor's commitment to the development of personalized medicine, AYAs up to 30 years of age (and in exceptional cases of relapsed pediatric tumors, beyond 30 years of age) will be included in the expansion stage of the study.

3.3.3 Rationale for Biomarker Assessments

The Sponsor is committed to the collection of biomarker samples in all clinical studies. The objective of biomarker profiling is to enable development of treatments specifically targeted for optimum patient benefit. The rationale for the planned biomarker analyses is explained below. However, because the body of knowledge of potential new biomarkers is evolving, the definitive list of analyses may be modified on the basis of new information.

This study will explore biomarkers associated with response to MEK inhibition in archival or fresh tumor tissue specimens obtained at baseline.

Given the genetic heterogeneity of the patients who will enroll in this study, the magnitude of response to MEK inhibition may be different in certain pediatric tumors. To identify candidate predictive biomarkers, molecular analyses of tumor tissue and plasma may include assessment of genetic and activation status of the targeted RAS/RAF/MEK/ERK pathway, potential escape mechanisms such as receptor tyrosine kinases and PI3K/PTEN pathways, and components of the tumor stroma (e.g., tumor infiltrating lymphocytes). These analyses may be conducted at the DNA, RNA, protein, and cell levels. In addition, expression of pathway-relevant prognostic biomarkers and alternative drug targets may be explored. These analyses are essential for the identification of patients who will benefit the most from cobimetinib.

It has been shown that tumor-specific mutations can be identified in plasma ('circulating tumor DNA'). Assessment of RNA and DNA may be evaluated in tumor tissue collected at baseline and plasma collected at baseline and during the study. Analysis and correlation of mutations in tumor tissue and plasma will help to further evaluate the option of using plasma for the detection of tumor-specific mutations.

3.4 OUTCOME MEASURES

3.4.1 Safety Outcome Measures

The safety outcome measures for this study are as follows:

- Incidence and nature of DLTs
- Nature, frequency, severity, and timing of adverse events, including serious adverse events and adverse events of special interest
- Changes in vital signs, physical findings, and clinical laboratory results during and following cobimetinib administration
- Growth patterns (relative to age-specific standards for height and weight) accounting for baseline growth of the patient
- Development patterns (relative to onset of menarche [for females] and pubertal changes) accounting for baseline development of the patient

3.4.2 Pharmacokinetic Outcome Measure

The PK outcome measure for this study is as follows:

- To characterize cobimetinib PK in pediatric patients, the following PK parameters following single and multiple doses will be estimated: maximum plasma concentration observed (C_{max}), T_{max} , total exposure (area under the concentration–time curve from 0 to 24 hours [AUC_{0-24}]), and apparent clearance (CL/F).

3.4.3 Efficacy Outcome Measures

The co-primary efficacy outcome measures for this study are as follows:

- ORR, defined as the percentage of patients with a complete or partial response for patients with measurable disease or neuroblastoma patients with evaluable disease at baseline, or a complete response for patients with non–measurable but evaluable disease at baseline (except neuroblastoma patients), on two consecutive occasions ≥ 4 weeks apart, as determined by the investigator using mINRC for patients with neuroblastoma (see [Appendix 3](#)), RANO criteria for patients with HGG (see [Appendix 4](#); Wen et al. 2012), for the RANO criteria for patients with LGG (see [Appendix 5](#)) and RECIST v1.1 for patients with other tumors (see [Appendix 6](#)).
- PFS, defined as the time from initiation of study drug to the first documented occurrence of disease progression, as determined by the investigator using mINRC for patients with neuroblastoma (see [Appendix 3](#)), RANO criteria for patients with HGG (see [Appendix 4](#); Wen et al. 2012), RECIST v1.1 for patients with other tumors (see [Appendix 6](#)), and RANO criteria for patients with LGG (see [Appendix 5](#)) in the expansion stage in addition to RECIST v1.1, or death from any cause, whichever occurs first

The secondary efficacy outcome measures for this study are as follows:

- DOR, defined as the time from the first tumor assessment that supports the patient's objective response to the time of disease progression, as determined by the investigator using mINRC for patients with neuroblastoma (see [Appendix 3](#)), RANO criteria for patients with HGG (see [Appendix 4](#); Wen et al. 2012), RECIST v1.1 for patients with other tumors (see [Appendix 6](#)), and RANO criteria for patients with LGG (see [Appendix 5](#)) in the expansion stage in addition to RECIST v1.1, or death from any cause, whichever occurs first
- OS, defined as the time from initiation of study drug to death from any cause

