4.5.5 Tumor and Response Evaluations

All known sites of disease must be documented at screening and re-assessed at each subsequent tumor evaluation. Full baseline tumor assessments should be performed within 28 days prior to initiation of study drug (Day 1 of Cycle 1). Baseline assessments will consist of the entire diagnostic workup consistent with the response evaluation system used for the specific tumor type. Tumor assessments must be performed during the last week of the even-numbered cycles (i.e., at the end of Cycles 2, 4, 6, 8, etc., prior to the start of treatment in the next cycle). *For patients who have not met study criteria for progressive disease after 12 cycles, subsequent response assessments should be conducted at Cycles 16, 20, 24, and every 6 cycles thereafter.* At the investigator's discretion, tumor assessments may be repeated at any time if disease progression is suspected.

Response will be assessed by the investigator on the basis of physical examinations, computed tomography (CT) scans or MRI scans and additional ¹²³I-MIBG imaging for neuroblastoma patients. The following response assessment systems will be used mINRC, RANO criteria for HGG, RANO criteria for LGG, or RECIST v1.1, as appropriate for the patient's diagnosis. CT or MRI scans should evaluate neck, chest, abdomen, and pelvic region if clinically indicated. MIBG scanning should be used for response assessments in neuroblastoma patients, if positive at baseline. PET scans may be performed at the discretion of the treating physician.

Any objective response must be confirmed by repeat assessments ≥ 4 weeks after initial documentation. The same radiographic procedure used to assess disease sites at screening should be used throughout the study (e.g., the same contrast protocol for CT scans). To the extent that is feasible, assessments should be performed by the same evaluator to ensure internal consistency across visits.

Patients with neuroblastoma must have a MIBG scan and bilateral bone marrow aspirates and biopsies done for disease evaluation. If the enrollment bone marrow aspirates and biopsies are negative for disease, subsequent bone marrow aspirates and biopsies are not needed. Patients with neuroblastoma should also have urine catecholamines (including homovanillic acid and vanillylmandelic acid) sent at screening and with all responses assessments.

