Appendix 2 Schedule of Pharmacokinetic and Pharmacodynamic Assessments

Visit	Timepoint	Sample Type
Cycle 1, Day 1	Prior to the dose	Plasma PK sample for cobimetinib + Plasma PD biomarker sample
	2 hr (\pm 30 min) after the dose	Plasma PK sample for cobimetinib
	4 hr (\pm 30 min) after the dose	Plasma PK sample for cobimetinib
	6 hr (\pm 30 min) after the dose	Plasma PK sample for cobimetinib
	24 hr (\pm 1 hr) after the dose, prior to dose on Day 2 of Cycle 1	Plasma PK sample for cobimetinib
Cycle 1, Day 21	Prior to the dose	Plasma PK sample for cobimetinib
	2 hr (\pm 30 min) after the dose	Plasma PK sample for cobimetinib
	4 hr (\pm 30 min) after the dose	Plasma PK sample for cobimetinib
	6 hr (\pm 30 min) after the dose	Plasma PK sample for cobimetinib
	24 hr (\pm 1 hr) after the dose	Plasma PK sample for cobimetinib
Cycle 2, Day 1	Prior to the dose (within 4 hr prior)	Plasma PK sample for cobimetinib
Cycle 2 (and every 2 cycles thereafter), Days 22–28	Samples should be collected on the day of scheduled tumor assessments.	Plasma PD biomarker sample
Study drug discontinuation	Any time during visit	Plasma PD biomarker sample

hr = hour; min = minute; PD = pharmacodynamics; PK = pharmacokinetic.

Note: Except for Day 1 of Cycle 1, all other study visits and assessments during the treatment period should be performed within 3 days of the scheduled date.

Appendix 3

Modified International Neuroblastoma Response Criteria

Below response assessment is modified from the original INRC publication in 1993.

DEFINITION OF MEASURABLE (EVALUABLE) DISEASE ON CT/MRI SCAN

The presence of at least one lesion that can be accurately measured in at least one dimension with the longest diameter at least 20 mm. With a spiral computed tomography (CT) scan, lesions must be at least 10 mm. The investigator will identify up to 10 measurable target lesions to be followed for response. Note that bone lesions will be considered as non-target lesions for evaluation of CT/magnetic resonance imaging (MRI) response since they will be evaluated with MIBG scans.

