Malignant Lymph Nodes. To be considered pathologically enlarged and measurable, a lymph node must be ≥ 15 mm in the short axis when assessed by CT scan (CT scan slice thickness recommended to be ≤ 5 mm). At baseline and in follow-up, only the short axis will be measured and followed. Serial measurements of lesions are to be done with CT or MRI. The same method of assessment used to characterize each identified and reported lesion at baseline should be used during follow-up.

RESPONSE CRITERIA FOR MEASURABLE DISEASE ON CT/MRI SCAN

The sum of the longest diameter (LD) for all target lesions will be calculated and reported as the disease measurement. The response of the CT/MRI lesions will be defined as outlined below:

- Complete response (CR): Disappearance of all target and non-target CT/MRI lesions
- Very good partial response (VGPR): Greater than 90% decrease of the disease measurement for CT/MRI lesions, taking as reference the disease measurement done to confirm measurable disease at study entry; non-target CT/MRI lesions stable to smaller in size
- Partial response (PR): At least a 30% decrease in the disease measurement for CT/MRI lesions, taking as reference the disease measurement done to confirm measurable disease at study entry; non-target CT/MRI lesions stable to smaller in size
- Progressive disease (PD): At least a 20% increase in the disease measurement, taking as reference the smallest disease measurement since the treatment started, or a new site of tumor; non-target CT/MRI lesions stable, smaller, or increased in size
- Stable disease (SD): Neither sufficient shrinkage to qualify for PR nor sufficient increase to qualify for PD taking as reference the smallest disease measurement since the treatment started; no new sites of disease

Appendix 3

International Neuroblastoma Response Criteria (cont.)

RESPONSE CRITERIA FOR MORPHOLOGIC BONE MARROW DISEASE

Only those patients with morphologic evidence of neuroblastoma by routine H and E staining (neuron-specific enolase [NSE] staining only is not evaluable) will be evaluable to assess bone marrow response.

- CR: No tumor cells detectable by routine morphology on two subsequent bilateral bone marrow aspirates and biopsies done at least 3 weeks apart after study entry.
- PD: Tumor seen on morphology on two consecutive bone marrows done at least 3 weeks apart in patients who had no tumor in bone marrow at study entry

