Patient may be declared to have PD in bone marrow after only one diagnostic bone marrow at the discretion of the treating physician

Patients who enter study with bone marrow tumor by morphology will be considered to have PD if there is a minimum of 25% tumor in the marrow by morphology and a doubling in the amount of tumor in the marrow compared with the level present at study entry. For example, a patient entering with 5% tumor in marrow by morphology must increase to >25% tumor to have PD; a patient entering with 30% tumor must increase to >60% tumor.

- SD: Persistence of an amount of tumor in the bone marrow by morphology that does not meet criteria for either CR or PD

Patients who clear morphologic tumor but have immunocytologic tumor will be called SD.

RESPONSE CRITERIA FOR MIBG-POSITIVE LESIONS

All patients with known MIBG-avid lesions will be evaluable for MIBG response following the first course of therapy. The following criteria will be used to report MIBG response:

- CR: Complete resolution of all MIBG-positive lesions
- PR: Resolution of at least one MIBG-positive lesion, with persistence of other MIBG positive lesions
- SD: No change in MIBG scan in number of positive lesions (includes patients who have same number of positive lesions but decreased intensity)
- PD: Development of new MIBG-positive lesions

Appendix 3

International Neuroblastoma Response Criteria (cont.)

DEFINITION OF OVERALL RESPONSE FOR EACH PATIENT WITH NEUROBLASTOMA

The International Neuroblastoma Response Criteria were developed to define responses in patients being treated with frontline therapy from diagnosis.¹ These criteria were utilized as a basis for the following response criteria, which integrate response at all sites defined as measurable in this study, including CT/MRI lesions that meet RECIST, MIBG-positive lesions, and bone marrow disease. These criteria will be used to define the overall response for each patient.

- CR: Disappearance of all target lesions; no evidence of tumor at any site (chest, abdomen, liver, bone, bone marrow, nodes, etc.); homovanillic acid (HVA) and vanillylmandelic acid (VMA) normal

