- VGPR: Greater than 90% decrease of the disease measurement for CT/MRI target lesions, taking as reference the disease measurement done to confirm measurable disease in target lesions at study entry; all preexisting bone lesions with CR by MIBG; MIBG scan can be SD or CR in soft tissue lesions corresponding to lesions on CT/MRI; CR in bone marrow; no new sites of tumor; HVA/VMA normal
- PR: At least a 30% decrease in the disease measurement for CT/MRI target lesions, taking as reference the disease measurement done to confirm measurable disease in target lesions at study entry; bone marrow with CR; MIBG with either PR or CR in bone lesions; MIBG may be SD or CR in soft tissue lesions corresponding to lesions on CT/MRI; HVA/VMA may still be elevated.
- PD: Any one of the following:
 - At least a 20% increase in the disease measurement for CT/MRI target lesions, taking as reference the smallest disease measurement recorded since the start of treatment
 - Appearance of one or more new lesions or new sites of tumor
 - PD as defined above for either bone marrow or MIBG lesions
- SD: Stable disease by either CT/MRI lesion, bone marrow, or MIBG criteria; no new lesions; no new sites of disease

The overall response as assessed at any particular timepoint based on the various disease sites is summarized in the table below.

¹ Brodeur GM, Pritchard J, Berthold F, et al. Revisions of the international criteria for neuroblastoma diagnosis, staging, and response to treatment. *J Clin Oncol* 1993;11:1466–77.

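### ORR counts a PR for neuroblastoma patients with evaluable disease, but Appendix 3 gives no overall PR without a CT/MRI target-lesion response, so a MIBG partial responder without a target lesion and with marrow clear or uninvolved has no overall category

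*Combined protocol and SAP*

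**What the plan says.** Section 3.4.3 and the synopsis treat neuroblastoma separately. A confirmed response counts if it is "a complete or partial response for patients with measurable disease or neuroblastoma patients with evaluable disease at baseline". Other tumors with only non-measurable disease need a CR. Section 4.1.1 admits disease followed by nuclear medicine, immunocytochemistry, tumor markers or another reliable measure. Section 4.5.5 adds that "MIBG scanning should be used for response assessments in neuroblastoma patients, if positive at baseline".

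Appendix 3 scores each site type first:
- On CT/MRI, "bone lesions will be considered as non-target lesions for evaluation of CT/magnetic resonance imaging (MRI) response since they will be evaluated with MIBG scans".
- The MIBG scale has a partial category: "PR: Resolution of at least one MIBG-positive lesion, with persistence of other MIBG positive lesions".
- Marrow has only CR, SD and PD, and is scored for "Only those patients with morphologic evidence of neuroblastoma by routine H and E staining".

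The overall criteria are described as ones "which integrate response at all sites defined as measurable in this study, including CT/MRI lesions that meet RECIST, MIBG-positive lesions, and bone marrow disease". Overall PR nevertheless opens with "PR: At least a 30% decrease in the disease measurement for CT/MRI target lesions", and also asks for marrow CR and MIBG PR or CR in bone lesions. VGPR needs a CT/MRI fall of more than 90%. Overall SD reads "SD: Stable disease by either CT/MRI lesion, bone marrow, or MIBG criteria", with no new disease. Table 1 of Appendix 3 has one PR row, whose CT/MRI entry is PR, and no row for a patient without a CT/MRI lesion.

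ORR is co-primary and investigator-determined, in the safety-evaluable population (Sections 6.5 and 6.5.1). Table 6 in Section 6.1 lists 10 patients and 3 responders for neuroblastoma, against a historical rate of 18%.

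**The concern.** Disease confined to bone and seen on MIBG has a scored site but no CT/MRI target lesion. It is the kind of disease that the neuroblastoma exception in Section 3.4.3 appears to be written for. The endpoint definition says a PR in such a patient counts; the criteria it relies on contain no way to assign one. SD does not catch the patient either, because a MIBG PR with clear or uninvolved marrow is not stable at any site.

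An investigator must then either drop the CT/MRI clause as not applicable and record PR, or follow the text and record no response. Two sites could classify identical scans differently, and the choice would be made after the scans are known. DOR (Section 6.5.2) starts from the same classification.

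**Working it through.** The plan states no figure on this point, so there is none to reproduce. The check applies the Appendix 3 prose to every non-progressing combination in a patient with no CT/MRI target lesion.

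**Inputs.** MIBG: CR, PR, SD or not involved. Marrow: CR, SD or not involved. Catecholamines: normal or elevated. MIBG is one axis because the soft-tissue allowance in Appendix 3 concerns lesions that correspond to CT/MRI lesions.

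**Number of combinations.** 4 × 3 = 12, less the one with neither site involved = 11; 11 × 2 = 22.

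| Combination | Count | Overall category |
|---|---|---|
| Every involved site CR, catecholamines normal | 3 | CR |
| MIBG SD (3 marrow states), or marrow SD with MIBG CR, PR or not involved (3): 6 × 2 | 12 | SD |
| MIBG PR, marrow CR or not involved: 2 × 2 | 4 | none |
| Every involved site CR, catecholamines elevated | 3 | none |

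Total: 3 + 12 + 4 + 3 = 22. Overall PR: 0.

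**Does Table 1 of Appendix 3 rescue these patients?** Read literally, it has no row for any of the 22. If an uninvolved site is entered as CR, the 15 CR and SD combinations find their rows and the same 7 still have none.

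**Where the gap stops.** If target lesions exist and are stable, the prose gives SD whatever MIBG shows. If marrow tumor falls without clearing, marrow is SD and so is the overall response.

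**Size in a 10-patient cohort.** One patient is 1/10 = 10 percentage points: 3/10 = 30% against 2/10 = 20%.

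To illustrate, suppose k of the 10 cannot be counted as responders and the rest respond independently with true rate p. Then

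P(at least 3) = 1 − Σ(i=0 to 2) C(10−k, i) pⁱ (1−p)^(10−k−i).

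| p | k = 0 | k = 2 | k = 3 | k = 5 |
|---|---|---|---|---|
| 0.18 (Table 6) | 0.263 | 0.161 | 0.115 | 0.044 |
| 0.40 (assumed) | 0.833 | 0.685 | 0.580 | 0.317 |

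The documents do not give k, and p = 0.40 is an assumption. The drops are upper bounds, because CR stays reachable without target lesions and an investigator may in practice assign PR.

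**The case against.** The strongest reply is that Appendix 3 works only if uninvolved sites are skipped. Overall PR also asks for marrow CR, yet marrow is scored only where there is morphologic tumor, and Section 4.5.5 does not require negative marrows to be repeated. Taken strictly, a patient with shrinking target lesions and clean marrow could not reach PR either. The exception in Section 3.4.3 makes sense only if the CT/MRI clause falls away when there is no such lesion, and Appendix 3 says it integrates all measurable sites. ORR can also be computed regardless: Section 6.5.1 counts those determined to have a response, so a patient with no category is by default a non-responder.

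Much of this stands. Skipping is the likely intent. But it is not written for CT/MRI, neither the PR sentence nor Table 1 of Appendix 3 provides it, and the default in Section 6.5.1 gives the opposite answer to the one Section 3.4.3 promises. The explicit non-responder rule there covers only patients with no post-baseline assessment.

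It also stands that the practical effect is uncertain. Expansion cohorts are chosen later, so a neuroblastoma cohort may not open. No formal hypothesis test is planned, further enrollment may be approved before the initial assessment, and expansion weighs other information (Sections 3.1.2 and 6.1).

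**Conclusion.** The conflict is real and should be fixed, but it is narrow. As written, Appendix 3 denies a PR that the co-primary endpoint says counts. It leaves 4 of 22 combinations (MIBG PR, marrow clear or uninvolved) without a category, and 3 more (all involved sites CR, HVA/VMA elevated). This rests on the prose definitions, for patients with no CT/MRI target lesion and no progression.

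Stronger readings that the documents do not support:
- A reader might infer that partial marrow responders are lost too. Appendix 3 has no partial marrow response; such patients are SD and properly non-responders.
- A reader might take all 7 combinations as MIBG partial responders, or 7/22 as a share of patients. Only 4 are MIBG partial responders, and the combinations carry no frequencies.
- A reader might conclude that evaluable-only patients cannot respond at all. Three combinations reach CR.
- A reader might call the 3-of-10 rule invalid. It is not a formal test, and the number affected is unknown.

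A smaller inconsistency sits in the same clause. Section 3.4.3 and the synopsis count a CR for non-measurable disease outside neuroblastoma, while Appendix 4 caps HGG with only nonmeasurable disease at stable disease. Because Section 3.4.3 takes HGG response from Appendix 4, the cap probably governs and no count need change.

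**What to change.** Before the first neuroblastoma interim analysis:

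1. State in the Appendix 3 overall-response text and its Table 1 that a site type not involved at baseline is not applied. For patients with no CT/MRI target lesion, define overall PR as: MIBG PR or CR if MIBG-positive at baseline; marrow CR if morphologically involved at baseline; non-target CT/MRI lesions stable or smaller; no new lesions or sites; HVA/VMA may still be elevated. Say openly that this is not the current PR sentence with a clause removed: the non-target and no-new-lesion conditions are carried over from elsewhere in Appendix 3, and the restriction of MIBG response to bone lesions is not kept. Where those two conditions hold, the 22 combinations become CR 3, PR 7, SD 12, none 0, and no CR or SD combination changes.
2. Beside the primary neuroblastoma ORR, report the count with only CR accepted in patients without target lesions. The reason is that MIBG PR needs just one resolved lesion. This is a sensitivity display only. It does not count single-lesion PRs, and it does not settle comparability with the 18% benchmark, for which Table 6 cites no source.
3. State that disease evaluable only by immunocytochemistry or tumor markers has no scored response in Appendix 3 and counts as non-response in ORR unless a criterion is defined in advance.
4. Reconcile Section 3.4.3 and the synopsis with Appendix 4 for HGG with nonmeasurable disease only.

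The cost is amendment wording and one extra line of output. MIBG, marrow and catecholamine results are already collected under Section 4.5.5. The drawback is that some counted PRs may rest on a small MIBG change.
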